13.1.3 Exposure and Compliance

Investigational product administration will be summarized in terms of each subject's dose, and in terms of duration of exposure for each period. Descriptive statistics for these quantities, including the mean, median, SD, minimum, maximum, and quartiles, will be provided by treatment group. Additionally, the number of subjects who are compliant with investigational product will be presented by treatment group for the Double-blind Period and overall for the OLE.

Subjects who taper to once-weekly application or who take a "drug holiday" will not be reported as having deviated from the protocol.

13.1.4 Efficacy Analysis

The ITT population will be used as the primary population for the primary analysis of efficacy at Week 12. Select efficacy analyses will be repeated as secondary analyses in the ITT and PP populations for the Double-blind Period. Efficacy analyses will also be repeated in the OLE using the OLE ITT, OLE mITT, and OLE PP populations. No formal inferential analyses will be conducted for efficacy variables in the OLE.

13.1.4.1 Efficacy Endpoints

Primary efficacy endpoint: The proportion of subjects in each treatment group who experience successful resolution of LI where "success" is defined as clear/almost clear overall and at least a 2-grade change from Baseline at Week 12/EOT in the Double-blind Period on the 5-point IGA scale.

Secondary: The secondary endpoints are as follow:

- The difference in mean scores between the active trifarotene cream HE1 and vehicle groups in the following assessment indices from Baseline through Week 12:
 - 5-point VIIS scale for scaling from Baseline through Week 12
 - Individual score for roughness (Scale: 0–4) overall
 - Palm/sole Assessment (Scale: 0–4)
 - Quality of life per DLQI and cDLQI
- The difference in proportion of subjects with presence of fissures on palm/soles (presence/absence, number of fissures, and pain associated with fissures [on a 0-3 scale]) at Week 12 between the active trifarotene cream HE1 and vehicle groups

Exploratory: The exploratory endpoints are as follow:

- The difference in mean ectropion scores (ESS of 0–8) between the active trifarotene cream HE1 and vehicle groups from Baseline through Week 12
- The difference in quality of life per EQ-5D-5L and EQ-5D-Y scores between the active trifarotene cream HE1 and vehicle groups from Baseline through Week 12

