
were compliant with study drug application, and who had no significant protocol deviations.
 
The PK population includes all subjects in the Safety Population who have at least 1 plasma sample with quantifiable concentration. The PK population will be used to summarize all PK endpoints.
 
The following populations are planned for the OLE of this study:
 
The OLE Safety population: all subjects who complete the 12-week Double-blind Treatment Period and receive at least 1 application of study drug in the OLE.
 
OLE ITT population: all subjects who complete the 12-week Double-blind Period and who sign the OLE informed consent.
 
The OLE mITT population: all subjects in the OLE safety population with at least 1 assessment of efficacy after Visit 6.
 
The OLE PP population: all subjects in the OLE mITT population who met all inclusion criteria and no exclusion criteria, were compliant with study drug application from baseline through EOT, and who had no significant protocol deviations throughout the study.
 
Subject Characteristics and Disposition: Descriptive statistics will be used to summarize demographic characteristics (age, sex, ethnicity, and race) and baseline characteristics for all enrolled subjects. Medical history, physical examination findings, and vital sign measurements for all randomized subjects will be presented in listings.
 
Efficacy Analyses: The number and proportion of subjects in each treatment group with successful resolution of LI by Week 12/EOT in the Double-blind Period will be presented. The primary efficacy endpoint will be analyzed using a logistic regression model with treatment and age group as factors. Other baseline characteristics and interactions may be included. The odds ratios and 95% CIs for the odds ratios will be presented. The difference in proportions between the active trifarotene cream HEI and vehicle cream groups, 95% CIs for the differences, and P-values for the differences in treatment will also be presented.
 
The IGA scores as well as secondary and exploratory efficacy endpoints will be analyzed by visit using descriptive statistics through Week 24. Change from Baseline through Week 12 will be presented and analyzed using a mixed model for repeated measures (MMRM). The model will include the change from Baseline score as the dependent variable, treatment group as a fixed effect, subject as a random effect, and Baseline score value as a covariate. Frequencies of results and 95% confidence intervals will also be reported, and scores will be analyzed as categorical variables using the Cochran-Mantel-Haenszel test. For subjects who report having fissures, the number of fissures and pain related to fissures will also be presented on a scale of 0-3 (none, mild, moderate, severe).
 
Clinical Pharmacology Analyses: Noncompartmental PK analysis will be performed for the PK subset of subjects, as data permit. Plasma concentrations of CD5789 and its major metabolites will be measured and will be listed by subject.
 
Safety Analyses: Safety and tolerability will be assessed based on the incidence of reported TEAEs, and SAEs, including relationship to study drug and severity, as well as physical examination findings, vital sign measurements (supine systolic blood pressure [SBP] and diastolic blood pressure [DBP] and pulse), clinical laboratory results (hematology, including serum aminotransferases and serum lipids, coagulation, clinical chemistry, and urinalysis) and 12-lead ECGs. Descriptive statistics for observed values and change from Baseline will be calculated at each visit within each study period and by treatment group within cohort.

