2.2. Schedule of Events

Table 2-1: Schedule of Events for Double-blind Period

	Screening (-35 days to -1 day) Washout up to 3 months ^a	Double-blind Treatment Period						
		Baseline (Day 1)	Telephone Visit (Day 7)	Day 14 ± 5 days	Day 30 ± 7 days	Telephone Visit (Day 45)	Day 60 ± 7 days	Day 90 ^{b,c} ± 7 days (ET)
Visit	1	2		3	4		5	6
Week		1		2	4		8	12
Written informed consent/assent	X							X ^a
Assign screening number	X							
Inclusion/exclusion criteria	X	X						
Demographics	X							
Medical history	X							
Physical examination	X	X ^d						X ^c
Vital signs (blood pressure and pulse)	X	X		X	X		X	X
Height, weight, and BMI	X							X
IGA assessment ^e	X	X		X	X		X	X
VIIS ^f assessment	X	X		X	X		X	X
Roughness assessment ^g	X	X		X	X		X	X
Palm/sole assessment	X	X		X	X		X	X
Palm/sole fissuring assessment ^h	X	X		X	X		X	X
Ectropion score	X	X		X	X		X	X
Photographs ⁱ		X			X			X
Quality of life per Dermatology Life Quality Index (DLQI)		X		X	X		X	X

	Screening (-35 days to -1 day) Washout up to 3 months ^a	Double-blind Treatment Period						
		Baseline (Day 1)	Telephone Visit (Day 7)	Day 14 ± 5 days	Day 30 ± 7 days	Telephone Visit (Day 45)	Day 60 ± 7 days	Day 90 ^{b,c} ± 7 days (ET)
Visit	1	2		3	4		5	6
Week		1		2	4		8	12
EQ-5D Quality of Life Questionnaire		X		X	X		X	X
12-lead ECG ^l	X	X			X			X
Clinical laboratory tests (hematology, chemistry, urinalysis) ^k	X	X			X			X
Serology (hepatitis B surface antigen, hepatitis C)	X							
Pregnancy test for female subjects (serum at Screening; urine subsequently) ^l	X	X			X		X	X
Randomization via IWRS		X						
PK blood sample collection ^m		X		X	X		X	X
Initial study drug application by clinic staff and measurement ⁿ		X						
Application instructions, advice on emollient and sunscreen use		X	X	X	X	X		
Dispense study drug and diaries ^o		X ^p		X	X		X	
Concomitant medications	X	X	X	X	X	X	X	X
Tolerability assessment		X		X	X		X	X
Adverse events (and review diaries)		X	X	X	X	X	X	X
Collect all used/unused study drug ^q				X	X		X	X
Provide information about OLE option					X	X	X	

Abbreviations: BMI = body mass index; DLQI = Dermatology Life Quality Index; ECG = electrocardiogram; ET = early termination; HEENT = head, eyes, ears,

nose, throat; ICF = informed consent form; IGA = Investigator's Global Assessment; IWRS = interactive web response system; OLE = open-label extension; PK = pharmacokinetic; WOCBP = women of childbearing potential; VIIS = Visual Index for Ichthyosis Severity

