8.2. Study Entry Criteria

8.2.1 Inclusion Criteria

A subject will be eligible for study participation if he or she meets all of the following criteria:

1. For Cohort A: subject is ≥ 18 years old; for Cohort B: subject is ≥ 12 years old.
2. Subject has known diagnosis of LI.
3. Subject has moderate to severe (IGA 3–4) LI on the IGA of LI severity.
4. Subject has signed an ICF at Screening before any investigational procedures. Subjects < 18 years of age (or Age of Majority) must sign an assent form in conjunction with an ICF signed by the parent/legal representative.
5. Subject who is participating in optional photography has signed a photography ICF.
6. Subject who is participating in the optional PK substudy has signed a PK ICF.
7. Subject is not of childbearing potential, i.e., a female who has not yet begun menstruating or who is postmenopausal (absence of menstrual bleeding for 1 year before Baseline, without any other medical reason, hysterectomy or bilateral oophorectomy),
OR
 - Subject is a woman of childbearing potential (WOCBP) or a male subject with sexual partners capable of reproduction who agrees to use 2 effective forms of contraception during the study and for at least 1 month after the last study drug application. The 2 authorized forms of contraception are condom used with 1 of the following methods of contraception:
 - bilateral tubal ligation
 - combined oral contraceptives (estrogens and progesterone) or implanted or injectable contraceptives with a stable dose for at least 1 month before Baseline; hormonal contraceptives must inhibit ovulation
 - hormonal intrauterine device (IUD) inserted at least 1 month before Baseline

OR

Agrees to abstain from heterosexual intercourse during study participation and for 1 month after the last application of study drug and to use a highly effective contraceptive as backup if he or she becomes sexually active during the study. Abstinence is only acceptable if this is the subject's usual lifestyle. Periodic abstinence (calendar, symptothermal, postovulation methods), withdrawal (coitus interruptus), spermicides only, and lactational amenorrhoea method are not acceptable methods of contraception.

AND

Male subjects may not donate sperm during the study and for at least 1 month after the last study drug application.

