10.2.2.1 Baseline Visit (Visit 2, Day 1)

The following procedures will be performed on Day 1 in the study clinic:

1. Review inclusion/exclusion criteria.

2. Record responses to DLQI and EQ-5D Quality of Life Questionnaires (see Sections 10.3.1.5 and 10.3.1.6 for which version of questionnaire to use).
3. Perform physical examination.
4. Record vital signs (blood pressure and pulse).
5. Record concomitant medications and concomitant therapies.
6. Record IGA.
7. Record VIIS.
8. Record roughness assessment.
9. Record palm/sole assessment.
10. Record palm/sole assessment of fissuring.
11. Record ectropion score.
12. At sites where the photographic substudy is conducted, take photographs of subjects who have provided informed consent for the photography.
13. Perform a 12-lead ECG.
14. Perform urine pregnancy test for WOCBP.
15. Collect blood and urine for routine laboratory tests (subject must be fasting; i.e., at least 8 hours).
16. Randomize via IWRS.
17. Collect a predose PK blood sample (all subjects).
18. Among subjects who consent to participate in the PK substudy, ensure that PK lines are placed before IP application. The IP will be applied in the clinic at this visit, and samples for PK will be taken at 1, 2, 4, 8, 12, and 24 hours postdose on Day 1.
19. Among subjects in the PK study, perform additional ECGs at times of serial sampling.
20. Clinic staff instructs subject on study drug application, applies initial study drug dose and measures amount used (i.e., study staff will weigh the 50-g tube before and after the first application to determine the fixed dose amount for each subject). If the product will be applied at home by someone other than the study subject, it is recommended that person assists with application at this visit to learn how the IP is applied.
21. Assess and record local tolerance/AEs.
22. Dispense study drug and diaries.
23. Advise subjects regarding permitted emollient(s) for use on nontreatment days; use of emollient(s) and/or sunscreen on study drug treatment days within 4 hours before or after study drug application is prohibited. Remind subjects that at least 24 hours must have elapsed since IP application before their next visit. Subjects should not to apply IP on visit days until after the visit.

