10.3.1.5 Palm/Sole Fissuring Assessment

Fissuring will be assessed by recording the presence or absence of fissures, the number of fissures present, and the pain associated with each fissure. A fissure is a longitudinal and deep crack that separates the stratum corneum and may penetrate down to the dermis, causing pain and sometimes bleeding. The subject will assess pain associated with fissures as ranging from 0-3 (none, mild, moderate, severe).

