13.1.4.3 Secondary Analyses

Secondary and exploratory efficacy endpoints will be analyzed separately for each period (Double-blind and OLE) using descriptive statistics.

Additionally, for the Double-blind Period only, change from Baseline in continuous secondary endpoints through Week 12 will be presented and analyzed using a mixed model for repeated measures (MMRM). The model will include the change from baseline score as the dependent variable, treatment group as a fixed effect, subject as a random effect, and baseline score value as a covariate.

For subjects who report having fissures, descriptive summaries of the number of fissures and pain related to fissures will also be presented by treatment group and body area for each period.

The DLQI scores will also be analyzed using descriptive statistics through Week 12.

The proportion of subjects with at least a 50% reduction in IGA score from Baseline will be analyzed using the same logistic regression analysis described in Section [13.1.4.2](#).

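### The Week 12 palm/sole fissure comparison makes no use of baseline fissure presence, which is recorded on every subject, so the between-arm difference is less precise than it could be

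*Protocol*

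**What the plan says.** All references are to the Amendment 1 text.

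- **Endpoint.** Section 13.1.4.1 lists "The difference in proportion of subjects with presence of fissures on palm/soles" at Week 12, between the active and vehicle groups. It is not restricted to subjects with fissures at entry, and no baseline term is mentioned.
- **Analysis.** Section 13.1.4.3: "Secondary and exploratory efficacy endpoints will be analyzed separately for each period (Double-blind and OLE) using descriptive statistics". The continuous secondary endpoints also get an MMRM with "treatment group as a fixed effect, subject as a random effect, and baseline score value as a covariate". The logistic regressions in Sections 13.1.4.2, 13.1.4.3 and 13.1.4.5 cover IGA, roughness and the palm/sole grade, not fissure presence. The synopsis adds that "scores will be analyzed as categorical variables using the Cochran-Mantel-Haenszel test", but this concerns scores and names no strata.
- **Data.** Table 2-1 schedules the "Palm/sole fissuring assessment" at Screening, Baseline and every double-blind clinic visit, and the Baseline Visit list includes "Record palm/sole assessment of fissuring". Section 10.3.1.5: "Fissuring will be assessed by recording the presence or absence of fissures, the number of fissures present, and the pain associated with each fissure".
- **Entry.** Section 8.2.1 requires "Subject has moderate to severe (IGA 3–4) LI on the IGA of LI severity". No criterion requires fissures, and Section 10.3.1.1 leaves palms and soles out of the IGA.
- **Randomization.** Section 9.6 describes permuted blocks and names no stratification factor.

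**The concern.** The Week 12 proportion mixes subjects who entered with fissures, and can lose them, with subjects who had none. Whether a subject had fissures at Baseline probably says a good deal about Week 12, and that information is already in the database. The plan uses the baseline score for every secondary endpoint analysed as a continuous measure, but states no use of it for this one.

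Two things are at stake. The confidence interval for the difference will be wider than it need be. And with about 40 subjects per arm, a chance difference in baseline fissure prevalence can make up a noticeable part of an observed Week 12 difference. Both apply to a purely descriptive report as well as to a formal test.

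**Working it through.** **Inputs from the protocol.** 120 subjects randomized 1:1:1, so 40 per arm; 32 evaluable per arm after 20% dropout (Section 13.2); two-sided 5% level (Section 13.1). Section 13.2 gives power for the primary endpoint only, so there is no stated fissure figure to reproduce.

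**Assumed inputs.** The protocol gives no fissure rates. Assumed here: baseline prevalence π = 40-60%; persistence to Week 12 of 80-90% on vehicle (a₀) and 40-60% on active (a₁); new fissures in those without any at Baseline c = 5-10%, the same in both arms. Taking π at 40, 50, 60; a₀ at 80, 90; a₁ at 40, 50, 60; and c at 5, 10 gives 3 × 2 × 3 × 2 = 36 scenarios.

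**1. Chance imbalance.** With no treatment effect (persistence a in both arms), the expected unadjusted Week 12 difference, given the baseline prevalences b₁ and b₀, is (a − c)(b₁ − b₀).

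- The factor a − c runs from 0.80 − 0.10 = 0.70 to 0.90 − 0.05 = 0.85.
- The SD of b₁ − b₀ at 40 per arm is √(2π(1 − π)/40): 0.110 at π = 40% or 60%, and 0.112 at 50%.
- A one-SD imbalance therefore shifts the Week 12 difference by 0.110 × 0.70 = 7.7 to 0.112 × 0.85 = 9.5 points.
- By exact binomial calculation, an imbalance of at least 10 points has a probability of 42-43%, and one of at least 15 points 21-22%.

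**2. Precision, worked example.** 40 per arm, π = 50%, persistence 80% versus 40%, c = 10%.

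- Week 12 proportions: vehicle 0.5 × 0.8 + 0.5 × 0.1 = 0.45; active 0.5 × 0.4 + 0.5 × 0.1 = 0.25.
- Unadjusted variance: (0.45 × 0.55 + 0.25 × 0.75)/40 = 0.01088, SE 0.104.
- Stratified variance, about 20 per arm per stratum and weight ½ each: ¼ × [(0.8 × 0.2 + 0.4 × 0.6)/20 + 2 × 0.1 × 0.9/20] = 0.00725. The random stratum weights add (0.4)² × 0.25/80 = 0.0005. Total 0.00775, SE 0.088.
- 95% half-width: 1.96 × 0.104 = 20.4 points unadjusted, 1.96 × 0.088 = 17.2 points stratified.

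**3. Power, only if a test were run.** Simulated unadjusted chi-square versus the Mantel-Haenszel test stratified by baseline presence:

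| Per arm | Scenario (π; a₀ vs a₁; c) | Unadjusted | Stratified | Gain (points) |
|---|---|---|---|---|
| 32 | 40%; 80 vs 60%; 10% (smallest gain) | 10.6% | 13.5% | 2.8 |
| 32 | 50%; 80 vs 40%; 10% | 39.9% | 50.7% | 10.8 |
| 32 | 50%; 90 vs 50%; 5% (largest gain) | 39.4% | 62.1% | 22.6 |
| 40 | 40%; 80 vs 60%; 10% (smallest gain) | 11.4% | 15.8% | 4.3 |
| 40 | 50%; 80 vs 40%; 10% | 46.6% | 60.1% | 13.6 |
| 40 | 50%; 90 vs 50%; 5% (largest gain) | 46.0% | 72.2% | 26.1 |

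Across the 36 scenarios and both sample sizes, unadjusted power runs from about 11% to 80%. With no treatment effect, the stratified test rejects in about 4.7-4.9% of trials and the unadjusted test in about 5.6-5.9%.

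**4. When baseline predicts weakly.** 32 per arm, π = 50%:

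- Vehicle 70% persistence and 30% new, active 40% and 15%: 48% unadjusted, 50% stratified.
- Vehicle 60% and 40%, active 30% and 20%: 57% and 56%.
- Vehicle 70% and 30%, active 40% and 30%: 25% and 24%.

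The gain is also small when nearly everyone has fissures at Baseline: at π = 90% and persistence 80% versus 40%, about 1 to 3 points.

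**The case against.** The best case for the plan has five parts.

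- **The endpoint wording does not exclude adjustment, and detail is left to the SAP.** Section 13.1.4.1 says what is compared, not that the comparison must be unadjusted, and Section 13.1 calls itself a summary. This stands as far as it goes: the SAP may already add a baseline stratum, and nothing in the protocol forbids one. But Section 13.1.4.3 does specify baseline adjustment for the continuous endpoints and gives fissure presence only descriptive statistics, so there is a stated analysis to improve.
- **No test is planned.** A reader might infer that the plan gives up a known amount of power. The documents do not support that: no test, power or fissure rate is stated, and the size depends wholly on assumptions. The loss of precision does not depend on a test.
- **The estimate is not biased.** A reader might infer bias from the missing adjustment. Under randomization the unadjusted difference is unbiased and its confidence interval allows for chance imbalance. An imbalance does not pass through in full either; it is scaled by persistence minus the new-fissure rate.
- **Baseline may predict less well than assumed.** Usual care of hands and feet may continue during washout (Section 9.8), and standard-of-care treatment of palms and soles is allowed after Week 4 on worsening (Section 9.8.1). Both can change fissure status in either arm. This is why the range must reach down to zero.
- **A related endpoint is already adjusted.** The palm/sole grade includes fissures in its levels (Section 10.3.1.4) and is among the scores that Section 13.1.4.3 adjusts for baseline. That reduces the consequence but does not replace an analysis of fissure presence itself.

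**Conclusion.** The point holds as a low-cost improvement to a secondary endpoint, not as an error that undermines the trial. The stated analysis leaves out a baseline measurement available on every subject, at some cost in precision and with exposure to chance imbalance. Under the assumed rates, and only if a test is run, stratifying gains about 3 to 23 points at 32 per arm and about 4 to 26 at 40. With weak prediction the gain is about zero, at worst about a 1-point loss. These figures rest on assumed prevalence, persistence and new-fissure rates, and should not be quoted without them.

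**What to change.** Add one sentence to Section 13.1.4.3 and carry it into the SAP: fissure presence at Week 12 is compared for each active arm versus vehicle by a risk difference with 95% CI, stratified by baseline fissure presence (Mantel-Haenszel weights, with the matching Cochran-Mantel-Haenszel test if a P value is wanted). Tabulate Week 12 presence by baseline presence within each arm, so that resolution and new fissures can be read separately.

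The stratified risk difference is preferable to a logistic model with treatment, age group and baseline presence. At 32 per arm and 50% prevalence, about 16 subjects per arm start without fissures, and a 5-10% rate gives only 0.8 to 1.6 new-fissure events per arm.

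The cost is the sentence and one table. No visits, subjects or measurements are added, and the all-subject endpoint is unchanged.

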13.1.4.2 Primary Analysis

For the Double-blind Period only, the number and proportion of subjects in each treatment group with successful resolution of LI by Week 12/EOT will be presented. The primary efficacy endpoint will be analyzed using a logistic regression model with treatment and age group as factors. Other baseline characteristics and interactions may be included. The odds ratios and 95% CIs for the odds ratios will be presented. The difference in proportions between the active trifarotene cream HE1 and vehicle cream group, 95% CIs for the differences, and P-values for the differences in treatment will also be presented.

Descriptive summaries (such as mean, standard error, median, minimum, and maximum) and the changes from baseline will be provided for IGA scores for both periods.

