9.6. Method of Assigning Subjects to Treatment Groups

In the double-blind, parallel-group, randomized period of the study, subjects who meet study entry criteria will be randomly assigned in a 1:1:1 ratio to trifarotene cream HE1 100 µg/g or 200 µg/g or vehicle cream. The randomization schedule will be computer generated using a permuted block algorithm and will randomly allocate IP to randomization numbers. The randomization numbers will be assigned sequentially through a central interactive web response system (IWRS) as subjects are entered into the study. Study center will not be a blocking factor in the randomization schedule.

Premier Research will prepare the randomization schedule before the start of the study. No one involved in the study performance will have access to the randomization schedule before the official unblinding of treatment assignments. No subject will be randomized into this study more than once.

In the OLE, all subjects will receive trifarotene cream HE1 200 µg/g.

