13.1.2.3 Demographics and Other Baseline Characteristics

These analyses will be conducted for the ITT and OLE ITT populations.

Demographic variables will include age, sex, race, ethnicity, height, weight, and BMI. Baseline subject characteristics will include medical history, physical examination findings, and IGA score.

Prior and concomitant medications will be summarized by randomized treatment group, by the number and percentage of subjects taking each medication, and classified using World Health Organization Drug Dictionary (WHO-DD) Anatomical Therapeutic Chemical (ATC) classes and preferred terms.

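### The primary logistic model does not name baseline IGA (3 vs 4), although it sets whether success needs a 2-grade or a 3-grade improvement; naming it would be nearly free.

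*Protocol*

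**What the plan says.** Under section 13.1.4.2 the primary endpoint is to be "analyzed using a logistic regression model with treatment and age group as factors. Other baseline characteristics and interactions may be included". The synopsis repeats the permission: "Other baseline characteristics and interactions may be included". Neither place gives a list or a selection rule.

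The other relevant parts of the protocol are:

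- **Entry (8.2.1):** "Subject has moderate to severe (IGA 3–4) LI on the IGA of LI severity".
- **Success (13.1.4.1):** "clear/almost clear overall and at least a 2-grade change from Baseline at Week 12/EOT".
- **Randomization (9.6):** "The randomization schedule will be computer generated using a permuted block algorithm". Allocation is 1:1:1. Study center is ruled out as a blocking factor, and no stratum for severity is stated.
- **Baseline characteristics (13.1.2.3):** "Baseline subject characteristics will include medical history, physical examination findings, and IGA score".
- **Secondary repeated-measures model (13.1.4.3):** includes the "baseline score value as a covariate".
- **Timing (13.1):** the SAP is to be written before database lock, and overall unblinding follows lock.

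**The concern.** For every eligible subject the 2-grade condition is redundant. Reaching IGA 0 or 1 from 3 or 4 already implies a change of at least 2 grades, so baseline IGA alone decides how far a subject must improve. A move from 4 to 2 is a 2-grade improvement and still a failure. That makes baseline IGA a plausible strong predictor of the primary outcome.

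Neither the stated randomization nor the named model takes account of it, although the secondary model does adjust for baseline score. At stake are some precision in arms of 32 to 40 subjects, protection when severity happens to fall unevenly between arms, and a clear statement of which odds ratio is being estimated.

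**Working it through.** **The plan's own figure.** Section 13.2 claims more than 80% power for a two-sided Fisher test, 70% vs 40%, 32 evaluable per arm. Full enumeration gives 61.9%, so the claim does not reproduce. That is a separate matter and carries no weight here. The reference below is the unadjusted logistic test, at about 70% to 74%.

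**Improvement required.** Baseline 3: 3 − 1 = 2 grades. Baseline 4: 4 − 1 = 3 grades.

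**Inputs.** From section 13.2: success 70% vs 40%, and 32 evaluable per arm (40 × 0.8). From section 13.1: two-sided 0.05. Assumed, because the protocol gives neither: half of subjects at baseline IGA 4, and a success odds ratio of 1 to 8 between baseline 3 and 4.

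**Power.** Simulation of one active arm against vehicle, with marginal rates held at 70% and 40% and age group left out for simplicity. Entries are unadjusted → adjusted for baseline IGA.

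| Odds ratio, IGA 3 vs 4 | Likelihood-ratio test | Wald test |
|---|---|---|
| 1 | 71.5% → 70.0% (−1.5) | 70.8% → 67.8% (−3.0) |
| 2 | not run | 73.4% → 71.7% (−1.7) |
| 3 | 70.1% → 71.6% (+1.5) | 72% → 72% (0) |
| 4 | not run | 73.7% → 73.3% (−0.4) |
| 5 | 71.7% → 75.6% (+3.9) | 71% → 73% (+2) |
| 8 | 71.7% → 79.6% (+7.9) | 70.7% → 74.3% (+3.6) |

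The likelihood-ratio rows use 6,000 trials each and the Wald rows 3,000 or 4,000. With 3,000 trials the error on one power figure is √(0.7 × 0.3 / 3000) ≈ 0.8 point, so single rows wander. Repeat Wald runs gave −2.4 at odds ratio 1 and about +5 at 8. A check with 40,000 trials per setting gave −2.3 to +0.7 across both tests for odds ratios 1 to 3, and +1.9 to +7.6 for 5 to 8.

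**Chance imbalance.** A gap of at least 20 points between two arms of 32 means 7 or more subjects (7/32 = 21.9%; 6/32 = 18.8%). With half at IGA 4, the IGA 4 count in one arm plus the IGA 3 count in the other is binomial (64, ½). The probability is 2 × P(at least 39) = 10.3%. At an odds ratio of 5 and a 40% vehicle rate, success is about 58% from baseline 3 and 22% from baseline 4 (mean 40%; odds ratio (0.58/0.42)/(0.22/0.78) ≈ 4.9). A 20-point gap then moves the unadjusted difference by 0.20 × (0.58 − 0.22) ≈ 0.07, or 7 points.

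**What the odds ratio means.** The marginal odds ratio is (0.7/0.3)/(0.4/0.6) = 3.50. Conditional on baseline IGA, the same marginal rates correspond to 4.06 if the predictor odds ratio is 4, and 4.92 if it is 8.

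**Validity of the test without baseline IGA.** Under the null, with 40 per arm, the unadjusted Wald test rejected in 5.1% to 5.8% of simulated trials. That is no clear inflation.

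**The case against.** The strongest reply is that nothing is barred. Section 13.1.4.2 permits other baseline characteristics, section 13.1.2.3 counts IGA among them, and section 13.1 calls this part a summary with details to follow in the SAP. That stands: the point is that baseline IGA is not named, not that it is excluded.

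Three stronger readings are tempting and should not be drawn.

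- **That the primary comparison is biased.** Omitting a prognostic covariate does not bias a randomized test, and chance imbalance is sampling error that the confidence interval already reflects. About 90% of arm pairs fall short of the 20-point gap.
- **That the open covariate clause lets the result be picked.** If the best of several covariate sets were chosen after seeing results, simulated type I error would rise from 4.5% for the fixed model to 6.4% (with or without IGA) or 8.0% (best of eight sets). The documented order is SAP, database lock, then unblinding, which is meant to prevent exactly that. A closed covariate list is also something a SAP commonly supplies.
- **That adjustment reliably raises power.** It does so only if baseline IGA is a strong predictor. The protocol gives no association and no share at IGA 4, and a moderate association yields nothing or a small loss under a Wald test.

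What remains is that the protocol names a primary model and leaves out the one covariate that its endpoint definition makes most relevant, while adjusting for baseline in the secondary model.

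**Conclusion.** The point holds as an improvement worth making, not as an error that invalidates the analysis. The mismatch between endpoint and model is certain from the text. The size of the gain is known only with medium confidence. With half at IGA 4 and 32 per arm, power changes by about −2 to +1 points for a predictor odds ratio of 1 to 3 and by about +2 to +8 points for 5 to 8, with Wald gains smaller than likelihood-ratio gains. Both the share at IGA 4 and the odds ratio are assumptions. Priority lies between optional and recommended.

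**What to change.** In section 13.1.4.2 and the synopsis, state the complete primary model as treatment + age group + baseline IGA (3 vs 4). Treat any other covariates and all interactions as sensitivity analyses.

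Report the standardised risk difference for each dose against vehicle from that model, averaging predicted success over the observed baseline distribution. State that the adjusted odds ratio is conditional and will be larger than the marginal one.

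Say which visit supplies the covariate. IGA is recorded at both Screening and Day 1, and section 13.1 allows baseline to come from Visit 1 or Visit 2.

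The analysis of at least 50% IGA reduction in section 13.1.4.3 would inherit the model by cross-reference. Adding the matching baseline score to the exploratory roughness and palm/sole models in 13.1.4.5 is optional.

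The change needs one sentence and no new data. Its downside is about 1 to 2 points of power if baseline IGA is unrelated or only weakly related to outcome.
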